### 2.2 Pre-Clinical Data

A large number of studies in the literature have described the ability of freshly isolated adipose cells and cultured adipose stem cells to improve healing in several small and large animal preclinical models of cutaneous wound healing including normal animals, diabetic mice, irradiated skin, mitomycin-treated wounds, and ultraviolet-treated skin. All investigators report improved wound healing parameters including increased wound closure rate, increased granulation tissue, and improved wound vascularity and perfusion.

Pre-clinical testing (animal and biocompatibility) of ADRCs and the Celution® System has demonstrated safety and biocompatibility across numerous animal models of human disease. Data with intravenous,

subcutaneous or topical (spray) administration show efficacy of ADRCs over a control group treated with vehicle alone (lactated Ringer's solution). Intravenous administration has the advantage of administration not having to be available at the time of grafting (i.e. can be delivered following completion of the surgical procedure) and potentially may treat more wounds via systemic delivery relative to only treating selected wounds via topical delivery. Complete pre-clinical animal and biocompatibility data are provided in the Celution® System Investigator's Brochure.

### 2.3 Clinical Data

The Celution® System is approved for use as a medical device in the European Union. Hundreds of patients have been treated with autologous ADRCs prepared using the Celution® System. These patients range in clinical indication from cardiovascular disease to soft tissue reconstruction following breast cancer therapy.

The RESTORE-2 study was a Phase IV (post-market) study evaluating safety and efficacy of ADRC-enriched fat transplantation in the treatment of subjects with breast deformities post segmental breast resection (lumpectomy) with or without radiation therapy. This prospective, single-arm, open-label, multi-center study enrolled 71 subjects with defects ranging from 25-150 mL at 7 European clinical centers. A minimum of 270 mL of adipose tissue were harvested by tissue aspiration. The efficacy data demonstrated high degrees of patient (75%) and investigator (85%) satisfaction following ADRC-enriched fat grafting to treat breast defects post-breast conservation therapy. The procedure was also shown to be safe and well tolerated. RESTORE-2 results provide evidence of safety and efficacy following ADRC delivery for subcutaneous soft tissue indications.

PRECISE was a prospective, double-blind, randomized, parallel group, placebo-controlled, sequential dose escalation study that evaluated the safety and feasibility of intramyocardial administration of ADRCs in subjects with chronic myocardial ischemia not amenable to revascularization. Following baseline electromechanical mapping, subjects received  $\leq 15$  intramyocardial injections of ADRCs (n=21; median dose of ADRCs  $42 \times 10^6$  per subject) or placebo (n=6: indistinguishable solution) in the area(s) of the heart with inducible ischemia. ADRCs were processed using the Cytori Celution® System. ADRC-treated subjects demonstrated improvement in maximum oxygen consumption relative to the control group. Adverse events and serious adverse events were equally distributed across all treatments groups.

The APOLLO Clinical Trial was a safety and feasibility study of ADRCs processed by the Celution® System and delivered via the intracoronary (IC) route in the treatment of subjects with ST-segment elevation myocardial infarction. This was a prospective, double-blind, 3:1 randomized (ADRC: Placebo), parallel group, placebo-controlled trial. A total of 14 subjects were enrolled and treated according to protocol, 10 subjects received ADRCs and four received placebo. The APOLLO study demonstrated that harvest of adipose for the purpose of processing and returning autologous ADRCs via the intracoronary infusion of  $20 \times 10^6$  ADRCs is a safe and practical procedure. ADRC-treated subjects following acute myocardial infarction yielded several promising efficacy signals including a  $> 50\%$  reduction in infarct size by MRI compared to placebo treatment.

The ADVANCE clinical study (NCT01216995) is a safety and efficacy randomized (2:1), 2-arm, placebo-controlled, double-blinded clinical study in patients with ST elevation acute myocardial infarction. The ADRCs were injected via the intracoronary route at a dose of  $20 \times 10^6 \pm 10\%$  or placebo. A total of 23 patients were enrolled, with 13 patients receiving ADRCs and 6 receiving placebo, with 4 subjects not analyzed. While the ADVANCE study did not demonstrate a therapeutic benefit for ADRCs

treatment in patients after STEMI other than a possible preservation on LV mass, the ADVANCE study did demonstrate intracoronary injection of ADRCs obtained via liposuction was well tolerated, with no test material- or injection procedure-related adverse events reported, and was not associated with an increased risk of Major Adverse Cardiac and Cerebrovascular Events (MACCEs).

The ATHENA trials are two ongoing prospective, double-blind, 2:1 randomized (ADRC: Placebo), placebo controlled trials in the United States investigating the safety and efficacy of ADRCs in subjects with heart failure due to ischemic heart disease. ADRCs (low or high dose) are administered directly into the myocardium during a left heart catheterization procedure via 15 injections. A total of 31 subjects were randomized prior to termination of enrollment. Tissue harvest in compromised cardiac subjects was demonstrated to be feasible and can be performed with an acceptable safety profile. One-year follow-up has indicated an improvement in health related quality of life with ADRCs relative to placebo; however, no physiologic changes through echocardiogram or SPECT testing were observed.

The ACT OA trial is an ongoing double-blind 2:1 randomized placebo controlled trial investigating the safety and feasibility of intra-articular injection of ADRCs in the treatment of osteoarthritis of the knee. The study completed enrollment of 94 subjects in June 2015. All subjects have completed the study. There have been no UADEs. Tissue harvest was demonstrated to be feasible and safe in all enrolled subjects.

The STAR trial is a phase III a double-blind placebo controlled study evaluating subcutaneous treatment with ADRCs for hand dysfunction resulting from scleroderma. The trial is enrolled with 88 subjects as of June 2016. No related unanticipated adverse events have been reported. The tissue harvest procedures and cell injections have been well tolerated without complications.

A summary of pre-clinical and clinical experience is provided in the Celution® System Investigator's Brochure.

### **3 RATIONALE**

Patients with thermal wounds often require intensive management and have the risk of incomplete wound closure, prolonged period to wound closure, dysfunctional tissue healing (i.e. contractures, keloids) and infection. Such injuries may ultimately lead to chronic pain and disability. For digits and limbs, progressive injury may result in amputation. In addition, more rapid and complete wound healing following acute burns could reduce other complications and decrease the time spent in specialized hospital units. Cells present within the subject's own adipose tissue, ADRCs have the potential to improve healing following thermal injury by potentially reducing inflammation, improving restoration of blood flow, and stimulating local repair cells. Preclinical studies performed by Cytori in a full thickness thermal injury porcine model have demonstrated local and systemic delivery of autologous ADRCs without a scaffold increase wound re-epithelialization. Using a similar model but with Integra® skin substitute, local delivery of ADRCs is associated with improved wound tissue vascularity and maturation. In previous clinical studies, these cells have a favorable safety profile in acute myocardial injury, heart muscle damage, breast deformity following lumpectomy, and OA of the knee.

### **4 STUDY DESIGN**

#### **4.1 Study Overview**

The RELIEF Trial is a prospective, open-label, parallel group, usual care controlled, multi-center randomized (2:1, active: usual care alone) safety and feasibility study targeting thermal burns. Subjects will have at least one deep partial or full thickness burn wounds of  $\geq 250 \text{ cm}^2$  that is to be autografted with a meshed split thickness skin graft (STSG). Subjects randomized to ADRCs will undergo small volume fat harvest (100 to 150 mL) performed at initiation of general anesthesia for scheduled burn surgery followed by intravenous delivery of ADRCs within 4 hours following completion of Celution processing. The lipoaspirate will be processed in the Celution® System to isolate and concentrate ADRCs.

Following informed consent and initial screening assessments, eligible subjects will undergo pre-operative testing. On the procedure day, subjects will be randomized to ADRCs (with usual care) or usual care alone. Low volume lipoharvest will only be performed on subjects randomized to ADRCs in order to obtain 100-150 mL lipoaspirate, which will then be transferred to the Celution® System for processing to isolate and concentrate ADRCs for same-day administration. All treatment will be delivered in a total volume of 10 mL which will be delivered by slow intravenous administration into a peripheral vein.

Following surgery, subjects will be evaluated at time of first dressing change, day 10 ( $\pm 2$ ) (only if wound dressing change planned) and weeks 2 ( $\pm 3$  days), 3 ( $\pm 3$  days), 4 ( $\pm 3$  days), 8 ( $\pm 7$  days), 12 ( $\pm 14$  days), 26 ( $\pm 14$  days), and 52 ( $\pm 21$  days).

All subjects will undergo digital photography of the wounds, clinical evaluations, microbiology and laboratory testing prior to and after the procedure as outlined in *Section 9.0, Study Visit Requirements*, and in the *Schedule of Procedures (Appendix A)*.

The 1st 5 subjects enrolled in active treatment will be observed for adverse events over a 7 day period. If no SAEs occur during that period, for that individual subject, the next subject enrolled in active treatment may be entered with the same 7 day observation period. The safety results of the first 5 subjects will be reviewed by the DMC and their evaluation will be used in conjunction with the clinical data collected to date, and if appropriate, to potentially remove the staggering approach to the study. Enrollment after the first 5 subjects may continue only after the DMC has completed its safety review and recommends continuation.

## 4.2 Study Population

The study population will include subjects with a 20% - 50% TBSA and at least one deep partial or full thickness burn wound with an area of  $\geq 250 \text{ cm}^2$  who will undergo an escharectomy and a planned autologous meshed STSG to the identified area(s).

The rationale for including subjects with TBSA of 20-50% is that these subjects often have meshed STSG, increasing their risk of wound contraction and scarring. Thus, they could benefit from ADRCs as an adjunctive therapy with the potential for enhancing the engraftment and healing process. These subjects, those between 20% - 50%, also tend to be more hemodynamically stable in that their fluid requirements are less than those with greater wound size area. This relative clinical stability earlier in their initial treatment phase may allow them to better tolerate the lipoaspiration procedure which serves as the source for the ADRCs.

## 4.3 Sample Size

Up to a total of 15 subjects will be enrolled. Each patient may contribute up to three qualified wound

areas for the analysis. If more than one wound is identified, each must be noncontiguous with the other(s). Therefore, between 15 and 45 wounds will be evaluated. Wound areas that have been treated with a biologic dressing such as Alloderm® or Integra® are not qualified for analysis. However, a wound area that receives excision and grafting as described in this protocol without the application of a biologic dressing may be qualified even if other wound areas in the subject are not qualified because they have been treated with a biologic dressing.

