### 4.7 Inclusion and Exclusion Criteria

#### 4.7.1 *Inclusion Criteria*

Subjects will be enrolled into this study only if they meet ALL of the following criteria:

1. Males or females,  $\geq 18$  to  $\leq 65$  years of age
2. BMI  $> 20$  kg/m^2
3. Burn TBSA 20% - 50%
4. At least one deep partial thickness and/or full thickness thermal burn  $\geq 250$  cm^2 on the arms, legs, back, abdomen or chest that is anticipated to be covered with a meshed autologous STSG and that has not been treated previously with a biologic dressing such as Alloderm® or Integra®
5. Ability to safely undergo adipose tissue harvest procedure that is anticipated to yield  $\geq 150$  mL of adipose tissue at a site that is free from infection
6. Donor site availability for skin graft harvest

7. Able to provide written informed consent, signed by either the patient or their legally authorized representative
8. Women and men of child-bearing potential agreeing to use contraception during the study. Acceptable methods include surgical sterility, IUDs, hormonal contraception or double barrier methods.

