## 5.4 Blinding Procedures and Safeguards

The “blinded party” (photographic assessor(s) with no knowledge of the subjects treatment assignment) are those involved in the independent evaluation of the wound digital photographs.

All others involved in the study are considered the “unblinded parties”, meaning those that will or may have knowledge of a patient’s treatment assignment.

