### ***8.7.2 Digital Photography***

Digital photographs of the target wounds must be taken shortly after application of the STSG. Images of wounds will be taken by using the Silhouette Star System in accordance with the detailed work instruction provided in the Study Manual. Digital photographs will be taken at a fixed distance of approximately 30 - 50 cm from the wound. A reference image to identify the location of the target wound(s) with reference to anatomical landmarks should also be captured at the time of grafting. Prior to imaging, a label (with date, Subject number, and wound identification) and ruler (to indicate the longest length and width) will be placed near each wound site (within the camera's field of view) to track and identify each image. Images will be captured from directly above the wound (approximately perpendicular to the center of the wound surface) and at an oblique angle (approximately parallel to the center of the wound surface) to show scar height above adjacent skin. For the oblique images, a scale will be placed within the frame and immediately adjacent to the wound and perpendicular to the scar to allow assessment of scar height.

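### Wounds qualify for analysis by what they receive at surgery, after open-label randomization, and no list of target wounds is fixed beforehand, so wound-level healing and scar comparisons can be biased

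*Protocol*

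**What the plan says.** Section 4.3 (Sample Size) sets the wound-level rule: "Wound areas that have been treated with a biologic dressing such as Alloderm® or Integra® are not qualified for analysis". It then says that "a wound area that receives excision and grafting as described in this protocol without the application of a biologic dressing may be qualified", even where other wounds in the same subject do not. It also gives the numbers: "Up to a total of 15 subjects will be enrolled", each with up to three qualified wounds, and "Therefore, between 15 and 45 wounds will be evaluated".

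Inclusion criterion 4 (section 4.7.1) applies before assignment and asks for at least one wound "anticipated to be covered with a meshed autologous STSG and that has not been treated previously with a biologic dressing". Section 5.2 places randomization within 2 hours before the scheduled STSG surgery. Section 4.1 describes the trial as open-label. Section 5.4 blinds only the photographic assessors: "All others involved in the study are considered the" unblinded parties.

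The surgeon's confirmation in section 8.6.1 concerns the patient going on to a skin graft, not individual wounds. Section 8.7.2 says: "Digital photographs of the target wounds must be taken shortly after application of the STSG", with a reference image locating each wound captured at the time of grafting. Section 10.5 defines ITT on randomized subjects.

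**The concern.** Randomization protects a comparison only if the units analysed are fixed before the arm is known, or are fixed by something the arm cannot influence. Here the healing and scar endpoints are measured on wounds, and a wound's place in the dataset depends on what is done to it in an operation that follows an open assignment. If biologic dressing use, or the choice of three wounds among more, depends on both the arm and the wound's prognosis, the two sets of wounds differ for reasons other than ADRCs.

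The protocol plans two-sided 0.05 comparisons of the efficacy variables (sections 10.1 and 10.3) and means the data to inform a larger trial (section 10.2). A distorted estimate would carry into that design. Blinded scoring of photographs does not help, because it masks the rating of submitted wounds and not the choice of which wounds are submitted.

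**Working it through.** **The plan's own figure.** 15 subjects × 1 wound = 15 and 15 × 3 = 45, so the stated range reproduces. At 2:1 this is 10 against 5 subjects, or 10–30 against 5–15 wounds. The floor of 15 assumes full enrolment and that every subject keeps at least one qualified wound. If k subjects lose their only qualified wound at surgery, the floor is 15 − k, while ITT still counts 15 subjects.

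**Order of events, from the text.**
1. Screening (8.6.1): eligibility needs one wound with an anticipated meshed graft. The list contains no entry for target wounds.
2. Randomization (5.2; also listed in 8.7): within 2 hours before surgery, open-label.
3. Surgery: each wound does or does not receive a biologic dressing. Under the second rule quoted from 4.3, this settles whether it can qualify.
4. After grafting (8.7.2): the first stated record of the target wounds.

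The Procedure Day list (8.7) and Appendix A also contain no step that records wounds before assignment. Sections 4.3 and 5.2 cap the number at three but give no rule for choosing when more qualify. Because ITT is defined on subjects, it does not keep a disqualified wound in the data.

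**Illustration of size.** All inputs except the subject numbers are assumptions, since the protocol gives no SD, correlation or rate of biologic dressing use. Assume no treatment effect, three candidate wounds per subject, wound SD 15 points, within-subject correlation ρ, and the worst wound lost in a share q of ADRC subjects and in no control subject.

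The expected minimum of three independent standard normal values is −0.846. Dropping the minimum raises the mean of the remaining two by 0.846/2 = 0.423 within-subject SDs. The bias in the arm's average subject mean is therefore

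bias = q × 0.423 × 15 × √(1 − ρ).

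For q = 1 and ρ = 0.3, 0.5, 0.7: 0.423 × 15 × 0.837 = 5.3; × 0.707 = 4.5; × 0.548 = 3.5.

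Rejection rates come from simulating a two-sided 5% t-test on subject means, 10 against 5 subjects, 40,000 trials per setting:

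| Share of ADRC subjects affected | Bias, points (ρ from 0.7 to 0.3) | Rejection with no true effect |
|---|---|---|
| 10% | 0.3–0.5 | about 5% |
| 25% | 0.9–1.3 | about 5% |
| 50% | 1.7–2.7 | about 5–6.5% |
| 100% | 3.5–5.3 | about 7–12% |

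If loss of wounds is unrelated to arm or to prognosis, the expected shift is zero.

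**The case against.** **Prior treatment only.** The first sentence quoted from 4.3 can be read as meaning dressings applied before enrolment, in line with inclusion criterion 4, which says so explicitly. That would make it a baseline criterion. The reading is fair for that sentence alone, but the sentence sets no cut-off and the next one turns on what the wound receives. Even on the prior-treatment reading, the choice of three wounds among more would still be open after assignment.

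**Wounds may be identified earlier.** Section 4.2 refers to identified areas and section 8.3 to selected burn areas. Section 8.7.2 times the photograph and does not say that wounds are first chosen then. Detailed instructions sit in manuals that are not shown. This stands as a caution: informal identification before surgery is plausible. But neither section gives a time, a rule or a record.

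**Scope.** Section 10.2 states that the trial is not powered to test hypotheses, and the primary endpoints are safety and feasibility. This stands and limits the importance of the point.

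**Keeping every listed wound in the analysis.** Graft take is a percentage of the area originally covered by the graft, and epithelialization is that of the graft. A wound with no autograft at the visit has no defined value for either. This also stands, so a blanket retention rule would not work.

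**Conclusion.** The concern holds as a gap in the design: the qualification rule and the order of events let a surgeon who knows the arm influence which wounds are analysed. It reaches percent epithelialization, graft take, complete closure and the wound-level exploratory healing and scar measures. It does not reach the primary safety and feasibility endpoints.

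A reader might infer that these comparisons are biased, or that the false difference would be 3.5 to 5.3 points with 7–12% rejection. The protocol does not support either. Bias requires that dressing use or wound choice depend on both arm and prognosis, and nothing in the text shows that it will. The largest figures need the worst wound to be lost in every ADRC subject and in no control, and need it to be recognisable at surgery; they are an upper bound. Under the assumed SD and correlations, the bias is about 1 point when a quarter of ADRC subjects are affected, and type I error stays near 5%. The main risk is a distorted estimate rather than a grossly inflated error rate.

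The change is still worth making before enrolment, because a later SAP cannot recover wounds that were never recorded before assignment.

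**What to change.** In sections 4.3, 5.2 and 8.6.1:

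- Before the assignment is revealed, record in the IWRS up to three noncontiguous target wounds chosen by a fixed rule, for example the largest eligible.
- Limit the biologic-dressing disqualification to treatment given before randomization.
- Analyse the listed wounds by assigned arm, and report by arm any that later receive a biologic dressing or no autograft.
- Include those wounds wherever the endpoint is defined for them, for example complete closure and the scar measures.
- For graft take and epithelialization of the graft, state how a listed wound without an autograft is handled, and add a sensitivity analysis.
- State that the range of 15 to 45 wounds assumes full enrolment and at least one qualified wound per subject.

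The cost is one form before randomization and a few listed wounds with off-plan coverage, which need the handling rule above. No change to the clinical use of biologic dressings is proposed.

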#### **4.4 Clinical Sites**

Considering the patient population is expected to have an overall large %TBSA, based on the general prevalence of this type of burn injuries in the US population, up to ten (10) regional burn centers within the United States will be selected to participate in the RELIEF Trial.

#### **4.5 Study Duration**

Enrollment is anticipated to be completed over 18 months. For each patient, the study duration will include a 12 month follow-up period. The total duration of the RELIEF Trial is estimated to be 30 months.

